8.4.2.1.2 Blood WBC and Differential Cell Counts

As with sputum, the emphasis is on the Eosinophils. These are expected to increase upon BAC challenge (i.e. increases on Placebo c.f. pre-BAC values), and GSK2245035 should “blunt” this increase (*a priori* it is not certain if the treatment effect is sufficiently strong that it causes decreases, rather than a reduced level of increase c.f. Placebo).

The analysis approach is similar to Section [8.4.2.1.1](#); except that the All Subjects population is to be used and the list of differential cell types from the Blood Haematology samples is different (no Macrophages, BEC or Total Non-Squamous Cells but Monocytes and Basophils are expected). Also and if present in the source data only the total Neutrophils should be descriptively summarised/analysed (not Segs and Bands). Total WBC should also be modelled.

8.4.2.1.3 Blood PBMC

NOT PART OF SAC DELIVERABLE: These samples will be stored and further processing would be subject to study outcome determined from the other endpoints (statistical analyses would be reported separately and methods documented in the corresponding write up / report). The Statistical analysis methodology depends upon what methodology is used to process the samples, as the data structure/content will depend on that choice.

8.4.2.1.4 FeNO (Exhaled Nitric Oxide)

This section has been written assuming that FeNO response will require a log transformation. If it is not the case then appropriate modification should be made (e.g. comparisons expressed as differences rather than ratios (fold changes)).

Statistical Analysis of “Direct BAC effect” FeNO Samples

- Tables of descriptive summary statistics and Figures of type PD_F1, PD_F2 and PD_F4
- A Bayesian repeated measures mixed effect model, with non-informative priors for all model parameters, will be fitted to each of the transformed responses collected from an individual subject (i.e. 8 data points per subject; the combinations of Visit and Sample times SV Pre-BAC, SV 24 Post BAC, FUV1 Pre-BAC, FUV1 24h Post BAC, FUV2 Pre-BAC, FUV2 24h Post BAC, FUV3 Pre-BAC and FUV3 24h Post BAC).
- For the purposes of assessing models R1 to R3 (see Section 11.9.1) consider “Visit” in those models to be a eight level term covering the data recorded per subject with these additional terms:

Fixed Categorical: Intercept

The repeated measures term is Visit (Subject = Subject), with an Unstructured variance covariance matrix common to each treatment arm (8x8).

- In this model parameterization the usual “Baseline” timepoints (Pre-BACs) are modeled as response variables and not covariates. Therefore posterior distributions for the quantities of interest; namely treatment effect on “within visit fold changes (Post/Pre) adjusted for the screening visit and placebo fold changes”; use fold changes representing the mean predicted response at the timepoint (and not the average of the individual subjects fold changes).
- The model can provide several layers of useful information that should be presented instead of the default set of comparisons. The following should be modified if the model form is “R1”. The Back transformed predicted response for each treatment arm (x2) and visit (x8) combination should be produced. The next stage is to determine the fold change of the predicted response (Predicted Post BAC / Predicted Pre-BAC) within each of the four visits (SV, FUV1, FUV2 and FUV3) for each treatment. For each treatment arm its respective SV fold change can be subtracted from the FUV1, FUV2 and FUV3 visits. This quantity can then be compared across the treatment arms (within each of FUV1, FUV2 and FUV3); to provide an estimate of the screening visit and placebo adjusted change in BAC induced response.

8.4.2.2 Biomarkers Supporting the NAC related exploratory objective(s)

The Background samples should be analysed separately from the others as their intent is to capture changes in condition over the season (longer term changes).

The Pre-NAC, 5min and 6 hours are designed to measure the direct (within day) impact of the NAC procedure. The pre-wash (applied as part of the process to obtain the background sample) should also make the pre-NAC values more consistent (essentially zero) and should ensure that subjects should begin from a similar nasal condition (i.e. with a clean nose). Thus challenge related changes should be more consistent as mediators induced by the challenge should be the dominant items detected.

However, although all post NAC samples may be collected, not all of the biomarker types will be evaluated in the first instance. Pre-NAC samples will be evaluated for all biomarker types (mast cell mediators and inflammatory mediators). Mast cell mediators will also be evaluated from the 5min sample and Inflammatory mediators will be also be evaluated for the 6h sample.

Whilst the statistical analysis may split the data initial summaries will be produced using the complete dataset (i.e. a “PD_F1” format Figure and summarised in descriptive tables).

8.4.2.2.1 Nasal Lavage Fluid & Nasal Lavage Filters

Nasal Lavage Fluid samples are expected to provide the Mast Cell Mediator results (plus ECP and allergen specific IgA). Nasal Filters are expected to provide the Inflammatory mediators (chemokines and cytokines).

Statistical Analysis of “Background” Samples

- Additional Figures of type PD_F3
- Separate Bayesian repeated measures mixed effect models (per analyte), with non-informative priors for all model parameters, will be fitted to each transformed response over the planned post Screening time points (FUV1 and FUV2).
- Baseline: (Transformed) SV Background
- The additional terms to include in the chosen “R” model (see Section 11.9.1) are:

Fixed Categorical: Intercept

Fixed Continuous Covariates: Baseline*Visit

The repeated measures term is Visit (Subject = Subject), with an Unstructured variance covariance matrix common to each treatment arm (2x2).

Statistical Analysis of “Direct NAC effect” Samples

- Additional Figures of type PD_F2 and PD_F4
- Separate Bayesian repeated measures mixed effect models (per analyte), with non-informative priors for all model parameters, will be fitted to each of the transformed responses collected from an individual subject (i.e. 6 data points per subject; the combinations of Visit and Sample times SV Pre-NAC, SV Post NAC, FUV1 Pre-NAC, FUV1 Post NAC, FUV2 Pre-NAC and FUV2 Post NAC; where Post-NAC is either 5m or 6h depending whether the biomarker is a mast cell mediator (5m) or inflammatory (6h)).
- For the purposes of assessing models R1 to R3 (see Section 11.9.1) consider “Visit” in those models to be a six level term covering the data recorded per subject with these additional terms:

Fixed Categorical: Intercept

The repeated measures term is Visit (Subject = Subject), with an Unstructured variance covariance matrix common to each treatment arm (6x6).

- In this model parameterization the usual “Baseline” timepoints (Pre-NACs) are modeled as response variables and not covariates. Therefore posterior distributions for the quantities of interest; namely treatment effect on “within visit fold changes (Post/Pre) adjusted for the screening visit and placebo fold changes”; use fold changes representing the mean predicted response at the timepoint (and not the average of the individual subjects fold changes).
- The model can provide several layers of useful information that should be presented instead of the default set of comparisons. The following should be modified if the model form is “R1”. The Back transformed predicted response for each treatment arm (x2) and visit (x6) combination should be produced. The next stage is to determine the fold change of the predicted response (Predicted Post NAC / Predicted Pre-NAC) within each of the three visits (SV, FUV1, and FUV2) for each treatment. For each treatment arm its respective SV fold change can be subtracted from the FUV1 and FUV2 visits. This quantity can then be compared across the treatment arms (within each of FUV1 and FUV2); to provide an estimate of the screening visit and placebo adjusted change in NAC induced response.

8.4.2.2.2 Nasal Scrapes

NOT PART OF SAC DELIVERABLE: These samples will be stored and further processing would be subject to study outcome determined from the other endpoints (statistical analyses would be reported separately and methods documented in the corresponding write up / report). Note: Nasal scrape data are not going to be processed as in previous GSK2245045 studies (i.e. not planning to obtain a gene expression panel); samples may be analysed by CHIP-Cytometry.

8.4.2.3 Biomarkers supporting the Induction of TLR7 (target engagement) exploratory objective(s)

8.4.2.3.1 Nasal Lavage

- Tables of descriptive summary statistics and Figures of type PD_F1, PD_F2 and PD_F5
- Separate Bayesian repeated measures mixed effect models (per analyte), with non-informative priors for all model parameters, will be fitted to each of the transformed post DV1 baseline responses collected from an individual subject (i.e. 5 data points per subject; the combinations of Visit and Sample times excluding DV1 Pre-Dose; namely DV1 24h Post Dose, DV4 Pre-Dose, DV4 24h Post Dose, DV8 Pre-Dose and DV8 24h Post Dose).
- Baseline: (Transformed) DV1 Pre-Dose
- For the purposes of assessing models R1 to R3 (see Section 11.9.1) consider “Visit” in those models to be the five level effect covering the data recorded per subject (excluding DV1 Pre-Dose) with these additional terms:

Fixed Categorical: Intercept

Fixed Continuous Covariates: Baseline*Visit

The repeated measures term is Visit (Subject = Subject), with an Unstructured variance covariance matrix common to each treatment arm (5x5).

- Only items 6 and 7 from the default set of cut-points (Table 14) should be evaluated for the each of the default within visit treatment comparisons.
- Appropriate combinations of the model parameters should be used to evaluate the following two additional comparisons of interest (all cut point items from Table 14 should be applied to

the posterior distributions obtained for these additional comparisons and also this one:

Posterior Probability the quantity (X) is $\{\text{NOT}[(0.8 \leq X \leq 1.25)]\}$

- 24h response at DV4 vs DV1 for the 20ng GSK2245035 arm (adjusting for equivalent changes on Placebo). This is equivalent to
“[20ng Post at DV4 / 20ng Post at DV1] / [Pbo Post at DV4 / Pbo Post at DV1]”
- Analogous comparison for DV8 Vs DV1
- The above additional comparisons are investigating if there is any evidence for gross amplification or tolerisation of the TLR7 induced responses after 4 and 8 weeks of weekly dosing, using the placebo data to adjust for any drift in the biomarker changes that may be caused by other factors (e.g. seasonal changes in allergen exposure).

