## 1. PROTOCOL SYNOPSIS FOR STUDY 205540

### Rationale

GSK2245035 is a highly selective Toll-like receptor 7 (TLR7) agonist that preferentially stimulates the induction of type I interferons. Intranasal (i.n.) administration of GSK2245035 in humans has been shown to cause immune changes in the upper airways milieu that may alter bystander immune responsiveness to aeroallergens and contribute to reduction of allergic reactivity in subjects with respiratory allergies.

In a 8-week repeat dose safety study (TL7116958) with i.n. GSK2245035 20 ng and 80 ng, target engagement was confirmed by dose-related increases in serum and nasal lavage interferon inducible protein-10 (IP-10) levels in subjects with symptomatic allergic rhinitis and mild asthma. Prolonged activation (up to 1 week in the serum and 3 weeks in nasal lavage) of the interferon (IFN)  $\alpha$  pathway was noted at the higher dose with no associated adverse effects during this follow-up period. Eight weekly doses of both 20 ng and 80 ng reduced nasal symptoms and allergic biomarkers after nasal allergen challenge and those reductions were sustained up to 3 weeks post treatment.

This study will assess whether TLR7-mediated pharmacology, with i.n. GSK2245035 20 ng administered weekly for a period of 8 weeks, will lead to reduced allergic reactivity in the lower airways in subjects with mild allergic asthma.

[figure not shown]

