Blood Samples for PBMC preparations	BAC induced allergic inflammatory cell populations	Blood PBMC	n/a	ZKW	Conditional on other study endpoints showing positive signals Reported outside of CPSR as data generation may take a long time	To be defined, analysis of BAC induced allergic inflammatory populations in PBMC.	To be defined, reduction in BAC induced allergic inflammatory populations in PBMC.

T&E procedure	"Informal" description / rationale for samples	Matrix	Functional Categories	Vendor (Δ)	Analyte(s)	Comments	
						Anticipated Placebo profile	Characteristics of Successful drug effect
Nasal lavage	Changes in time (Background timepoint) Direct NAC effects	Lavage	Immuno-globulins Eosinophil mediators	GSK (Stevenage)	Background Pre-NAC & 6h Post NAC samples only (Allergens are "Birch", "House Dust Mite", "Cat" and "Grass" – Expecting one result per subject using the allergen they were challenged with – but re-label to "Allergen Specific IgA" for displays; only German sites expected to provide Birch Allergen data) ECP, Allergen Specific IgA	NAC should increase inflammatory mediators	Treatment related changes compared to screening of either background levels or the NAC induced increase at 6 hrs (6h/Pre-NAC ratio) Eosinophil mediators should go down or not increase on NAC if drug is working & IgA should increase
			Mast Cell mediators	GSK (Stevenage)	Pre-NAC & 5m Post NAC samples only Histamine Tryptase Conditional:	Mast cell mediators should increase in 5 min post NAC sample	Reduction in the NAC (5 min/pre-NAC ratio) induced response after treatment

T&E procedure	"Informal" description / rationale for samples	Matrix	Functional Categories	Vendor (Δ)	Analyte(s)	Comments	
						Anticipated Placebo profile	Characteristics of Successful drug effect
					Prostaglandin D2		compared to the SV
	TLR7 Induced changes (confirm target engagement)	Lavage	"TLR7" Target engagement	GSK (Stevenage)	IP-10	Within visit ratio (24h / Pre-dose) should be approximately one	Increase in within visit fold changes to confirm target engagement. Investigate whether the magnitude of fold changes at DV4 and DV8 are similar

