Nasal filter collection	Changes in time (Background timepoint) Direct NAC effects	Nasal Lining fluid	Inflammatory mediators	GSK (Stevenage)	Background Pre-NAC & 6h Post NAC samples only IL-5 IL-16 Conditional: IL-13, IL-33, TSLP, Eotaxin, MDC, TARC, IL-10, IFNg	NAC should increase inflammatory mediators	Treatment related reduction (compared to screening) of either background and or reduction of NAC 6h induced response. Th2 cytokines should all go down if drug is working Th1/Treg cytokines should increase

T&E procedure	"Informal" description / rationale for samples	Matrix	Functional Categories	Vendor (Δ)	Analyte(s)	Comments	
						Anticipated Placebo profile	Characteristics of Successful drug effect
			Mast Cell mediators	GSK (Stevenage)	Pre-NAC & 5m Post NAC samples only Histamine, Tryptase, Conditional:Prostaglandin D2 Note: Data generation conditional on sufficient sample remaining. Would only be assayed if mast cell mediators cannot be detect in Nasal lavage fluid samples	Mast cell mediators should increase in 5 min post NAC sample	Reduction in the NAC (5min/pre-NAC ratio) induced response after treatment compared to the SV

T&E procedure	“Informal” description / rationale for samples	Matrix	Functional Categories	Vendor (Δ)	Analyte(s)	Comments	
						Anticipated Placebo profile	Characteristics of Successful drug effect
Nasal scrape	Changes in time	Nasal Cells	n/a	ZKW	Samples to be held by ZKW, if we are able to get good samples and study is positive will be analysed. Reported outside of CPSR as data generation may take a long time	n/a	n/a
Genetic sample	PGx	Blood	Whole blood	GSK (Stevenage)	Stored for genomic DNA can only be used if individual consent is signed, could be used to see why someone is a non-responder	n/a	n/a
Blood sample for biomarker analysis	TLR7 Induced changes (confirm)	Serum	“TLR7” Target engagement	Q2	IP-10, IFNa, IFNb, IL-1b, IL-6, TNFa, MCP-1	Within visit ratio (24h / Pre-dose) should be approximately one	Increase in within visit fold changes to confirm target engagement

T&E procedure	“Informal” description / rationale for samples	Matrix	Functional Categories	Vendor (Δ)	Analyte(s)	Comments	
						Anticipated Placebo profile	Characteristics of Successful drug effect

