8.4.3.1 Correlation between Sputum and WBC cell differentials

Using the Sputum population scatterplots of BAC Sputum and WBC Differential cell results (both absolute counts and percentage variables) will be produced for each cell differential evaluated that is comparable over both sampling matrices. Simple linear regression lines may be overlaid onto the plot for i) each individual treatment arm and ii) all data combined (i.e. these would be simple regressions that do not account for the repeated measures on individuals when estimating the regression parameters and are intended to act as a rough indicator for how translatable conclusions drawn from analyses of WBC Differentials may be to the lung (BAC Sputum)). The plots will display all of the available data from all visits.

8.4.3.2 Defining responder / non-responder status for an individual subject using only their datapoints

For each subject the criteria in [Table 15](#) will be evaluated. If the endpoint relating to a question is missing then the subject's response will be set to missing and they would not contribute to the denominator when deriving any proportions.

Table 15 Criteria to be derived/applied at an individual subject level

ID	Area	Question(s)	Statistical Population	Endpoint(s)	Criteria / Responder algorithm (for non-missing endpoints)	Expected rate on Pbo Arm
A1	Target Engagement	Sustained activation of GSK2245035 target pathway?	Per Protocol	Within visit fold change in Nasal Lavage IP-10 (24h / Pre-Dose) at DV1 and DV8	Yes: Fold change ≥ 2 for BOTH DV1 and DV8 visits No: Any other outcome	<5% from 3x Previous studies (TL7114450, TL7116392, TL7116958)
B1 (FUV1) B2 (FUV2) B3 (FUV3)	Clinical BAC endpoint(s)	At least 20% attenuation of LAR Response c.f. SV?	Per Protocol	FUV1: WM and Min LAR FEV1 absolute change from saline FUV2: WM and Min LAR FEV1 absolute change from saline FUV3: WM and Min LAR FEV1 absolute change from saline	Derive Separately for each FU Visit Yes: $\geq 20\%$ Attenuation (c.f. SV) observed for either WM or Min LAR endpoint No: Any other outcome	~40% from 8x Historical GSK Allergen challenge studies (EL11002, HZA113126, INO102141, IPA101985, LPA111834, RES104385, RES114748 and SIG110762)

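### The modelled amplification/tolerance contrast for nasal lavage IP-10 compares 24 h levels, while SAP Table 12 asks about within-visit fold changes; the two differ by any trough carry-over

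*SAP*

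**What the plan says.** Table 12 (SAP 8.4.1) describes the nasal lavage IP-10 marker as a ratio taken within each visit. For placebo it expects: "Within visit ratio (24h / Pre-dose) should be approximately one". For a working drug it looks for a rise in that ratio and adds: "Investigate whether the magnitude of fold changes at DV4 and DV8 are similar".

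SAP 8.4.2.3.1 fits a repeated measures model to five post-baseline values (DV1 24 h; DV4 pre-dose and 24 h; DV8 pre-dose and 24 h), with DV1 pre-dose as covariate. It then specifies two cross-visit contrasts. The DV4 one is "24h response at DV4 vs DV1 for the 20ng GSK2245035 arm (adjusting for equivalent changes on Placebo", written out as "20ng Post at DV4 / 20ng Post at DV1] / [Pbo Post at DV4 / Pbo Post at DV1"; the DV8 one is analogous. Their stated purpose is to look for "any evidence for gross amplification or tolerisation of the TLR7 induced responses after 4 and 8 weeks of weekly dosing". All Table 14 cut-points apply to them, together with the posterior probability of lying outside 0.8 to 1.25. The placebo term is there to absorb drift from other causes, such as season.

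SAP 8.4.2.3.2 carries the approach to serum, for DV8 only. The serum row of Table 12 asks only for "Increase in within visit fold changes to confirm target engagement" and poses no cross-visit question.

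**The concern.** The DV4 and DV8 pre-dose values are modelled but do not enter the contrast. Dosing is weekly (Protocol 4.2), so these samples are roughly one-week troughs after the third and seventh doses. If the pathway is still partly active at that point, the 24 h level on active starts from a higher floor. It can then rise with no change in what each dose induces, or hold steady while induction falls. Placebo subjects have no drug-driven floor, so dividing by placebo does not correct for it.

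At stake is whether the plan can answer its own question about the induced response. For BAC sputum, BAC FeNO and NAC samples (8.4.2.1.1, 8.4.2.1.4, 8.4.2.2.1) the SAP does build modelled contrasts of post/pre fold changes across visits and arms. The target-engagement markers have none.

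**Working it through.** The documents give no expected value, power or sample size for this contrast, so there is no figure to reproduce.

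**Inputs from the documents.** The contrast formula, the DV1 pre-dose covariate and the 0.8 to 1.25 band (SAP 8.4.2.3.1); weekly dosing (Protocol 4.2); 20 completers per arm (Protocol 4.3).

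**Assumptions, because the documents give no figure.** Trough ratio C of 1 to 3; SD of log2 IP-10 of 0.5, 1.0 or 1.5; within-subject correlation 0.5; 4-fold induction at DV1; flat placebo.

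**Step 1: the identity.** Let A and P be the back-transformed model means on active and placebo, and v be DV4 or DV8.

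- Planned level ratio: `L = (A.post.v / A.post.1) / (P.post.v / P.post.1)`
- Induction ratio: `I = [(A.post.v / A.pre.v) / (P.post.v / P.pre.v)] / (A.post.1 / P.post.1)`
- Placebo-adjusted trough: `C = A.pre.v / P.pre.v`

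Multiplying out, `L = I × C`. DV1 pre-dose cancels because both arms are predicted at the same baseline.

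**Step 2: point values.**

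| C | L if induction is constant (I = 1) | I that gives L = 1.0 |
|---|---|---|
| 1 | 1.0 | 1.0 |
| 1.1 | 1.1 | 0.91 |
| 1.25 | 1.25 | 0.80 |
| 1.5 | 1.5 | 0.67 |
| 2 | 2.0 | 0.50 |
| 3 | 3.0 | 0.33 |

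Any C above 1.25 moves a constant induction out of the band. A fall in induction by a factor 1/C is cancelled exactly.

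**Step 3: posterior probabilities.** There were 2000 simulated trials per setting, 20 per arm, on the log2 scale, with DV1 pre-dose as covariate, no centre effect and a flat-prior t posterior. Entries are the median posterior probability of lying outside 0.8 to 1.25, level contrast / post/pre contrast.

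| Truth | SD 0.5 | SD 1.0 | SD 1.5 |
|---|---|---|---|
| I = 1, C = 1 | 0.11 / 0.22 | 0.44 / 0.55 | 0.61 / 0.70 |
| I = 1, C = 1.5 | 0.95 / 0.23 | 0.80 / 0.56 | 0.75 / 0.70 |
| I = 1, C = 2 | 1.00 / 0.24 | 0.98 / 0.56 | 0.92 / 0.69 |
| I = 0.67, C = 1.5 | 0.11 / 0.89 | 0.43 / 0.76 | 0.60 / 0.76 |
| I = 0.50, C = 2 | 0.11 / 1.00 | 0.43 / 0.95 | 0.60 / 0.88 |

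The first row shows the cost of the post/pre contrast: with nothing happening, it puts more probability outside the band because it is less precise. At SD 1.5 neither contrast separates the scenarios well.

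**Step 4: a case against using post/pre alone.** Hold placebo flat at 100. Let active go from 100 to 300 at DV1 and from 200 to 400 at DV8. Then L = 400/300 = 1.33, I = (400/200)/(300/100) = 0.67 and C = 200/100 = 2; the check is 0.67 × 2 = 1.33. The absolute rise is 200 on both occasions. One ratio reads as amplification and the other as tolerance, and both readings come from the trough.

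**The case against.** Several counter-arguments stand and limit the point.

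- **Carry-over at the study dose is not shown.** The Protocol synopsis reports "Prolonged activation (up to 1 week in the serum and 3 weeks in nasal lavage" at the higher dose. Protocol 4.5 says that sustained nasal activation to 3 weeks was seen only at 80 ng. That does not exclude a one-week trough at 20 ng, but no figure is given.
- **Within-visit fold changes are not absent from the plan.** Figure type PD_F5 plots them against each visit's own pre-dose value for nasal lavage and serum. A reader might infer that the plan computes only the level comparison; what is missing is the modelled version.
- **The trough will be visible.** SAP 8.4.2 already requires the posterior active/placebo ratio, with median and 95% credible interval, at each planned time point. For these markers only the cut-points are cut back, to items 6 and 7.
- **Stakes are low.** This is an exploratory look for gross effects, no decision rule attaches to the band, and SAP 11.11.1 lets posterior quantities be added.

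A reader might also think that Table 15 item A1 (SAP 8.4.3.2) is faulty. It requires "Yes: Fold change ≥ 2 for BOTH DV1 and DV8 visits", and a raised trough inflates the denominator. The documents do not support changing it. A1 uses only the subject's own data, so it has no placebo correction, and the same-visit denominator protects it from seasonal drift. Its expected placebo rate of under 5% is given for that definition. Faulting A1 for using post/pre would also contradict the case for adding post/pre here.

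None of this supplies the missing contrast. The figure and the pre-dose ratios let a careful reader suspect carry-over, but they correct neither the ratio nor its posterior probabilities.

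**Conclusion.** The point holds for nasal lavage IP-10 as a minor mismatch between the question in Table 12 and the contrasts modelled in 8.4.2.3.1. The discrepancy is exactly the placebo-adjusted trough ratio. It is zero if 20 ng leaves no trough at one week, and enough to move a constant induction out of the band if that ratio exceeds 1.25. Which applies is unknown; the trough values, SDs and correlation above are assumptions.

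Two stronger conclusions are not supported. The first is that the level ratio is wrong and post/pre should replace it. The level ratio is a valid summary of 24 h levels if labelled as such, and post/pre is less precise and falls when the trough rises under an unchanged absolute increase. The second is that serum conflicts with Table 12. The same arithmetic applies there, but Table 12 does not ask the cross-visit question for serum.

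**What to change.** In SAP 8.4.2.3.1, from the model already planned:

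1. Add, for DV4 and DV8, `{[20ng Post/Pre at v] / [Pbo Post/Pre at v]} / [20ng Post DV1 / Pbo Post DV1]`, with the same cut-points and 0.8 to 1.25 probability as the existing contrast.
2. Add a DV8 versus DV4 version, `{[20ng Post/Pre DV8] / [Pbo Post/Pre DV8]} / {[20ng Post/Pre DV4] / [Pbo Post/Pre DV4]}`, because Table 12 can be read as comparing those two visits with each other.
3. Keep the existing contrasts and label them as ratios of 24 h levels.
4. State that both are read beside the DV4 and DV8 pre-dose active/placebo ratios already planned, and that neither is used alone.

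The DV8 addition may also be made for serum (8.4.2.3.2), on the arithmetic alone. Leave Table 15 A1 as it is.

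The cost is a few extra lines of posterior output, with no new samples or assays. The drawback is the wider posterior of the post/pre contrast.
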